The study will be a non-interventional, descriptive, and longitudinal prospective study with primary data collection that involves sites/investigators. The patients must be diagnosed before enrollment with ATTR-CM and prescribed with tafamidis following the indications approved by National Institute for Drug and Food Vigilance (INVIMA) in Colombia. The patients will be followed up from the index date until patient i) have deceased, ii) have decided to withdraw from the study, iii) have terminated of treatment, iv) have been lost to follow up, or v) finalize the 24 months of following up. The index date will be defined as the date for the first prescription of tafamidis.

The patients who have been prescribed with tafamidis before August of 2023 will be recruited. The quality of life will be evaluated when the patient accepts to participate and signs the informed consent.

Quality of life, adherence, concomitant treatment, hospitalization for any causes, cardiovascular functionality will be measured 24 months after the prescription of tafamidis. Twelve months before the index date, treatments, and frequency of hospitalization for any causes will be measured (Table 1).

PFIZER CONFIDENTIAL

CT24-WI-GL02-RF01 6.0 Non-Interventional Study Protocol Template For Primary Data Collection Study 01-

Aug-2023

Page 11 of 57

**CLINICAL AND MEDICAL CONTROLLED DOCUMENT (CMCD)
REQUIRED FORM/TEMPLATE**

Identifier	Version	Title	Effective Date
CT24-WI-GL02-RF01	6.0	NON-INTERVENTIONAL STUDY PROTOCOL TEMPLATE FOR PRIMARY DATA COLLECTION STUDY	01-Aug-2023

There will be two sources of information. Clinical and demographic information at the baseline will be abstracted from the medical record while the data related to hospitalizations, cardiovascular functionality, quality of life, and deaths will be collected directly from the patients using validated questionnaires and structured interviews. Thus, in this case the report form (CRF) will serve as a source document.

The patients will be reached out to every three months±15 days through a phone call by a healthcare professional of the site. During this interview, the professional will perform a standardized interview with structured questionnaires to guarantee that the data collection process will be harmonized among patients. The interview could be in the site if the patient received clinical care there or she decided to move to it. Both collection data are completely accepted in the study.

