6. MILESTONES

Milestone	Planned date
Completion of feasibility assessment	12 May 2023
Registration in the EU PAS register	15 October 2023
Start of data collection	15 November 2023
End of data collection	30 July 2025
Start date of data analysis	16 September 2024
Study progress report 1	30 August 2024
Interim report 1	30 July 2024
Interim report 2	15 January 2025
Final study report	15 January 2026

PFIZER CONFIDENTIAL

CT24-WI-GL02-RF01 6.0 Non-Interventional Study Protocol Template For Primary Data Collection Study 01-Aug-2023
Page 17 of 57

CLINICAL AND MEDICAL CONTROLLED DOCUMENT (CMCD) REQUIRED FORM/TEMPLATE

Identifier	Version	Title	Effective Date
CT24-WI-GL02-RF01	6.0	NON-INTERVENTIONAL STUDY PROTOCOL TEMPLATE FOR PRIMARY DATA COLLECTION STUDY	01-Aug-2023

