9. RESEARCH METHODS

9.1. Study design

The study will be a non-interventional, descriptive, and longitudinal prospective study with primary data collection that involves sites/investigators. The patients must be diagnosed before enrollment with ATTR-CM and prescribed with tafamidis following indications approved by National Institute for Drug and Food Vigilance (INVIMA) in Colombia. The patients will be followed up from the index date until patient i) have deceased, ii) have decided to withdraw from the study, iii) have terminated of treatment, iv) have been lost to follow up, or, v) finalize the 24 months of following up, the event that happens first. The index date will be defined as the date for the first prescription of tafamidis.

The patients that were prescribed with tafamidis before August of 2023 will be recruited. In the cases where the patients were prescribed before starting the study, all previous information will be collected from the data provided by the patients. The quality of life will be evaluated when the patient accepts to participate and signs the informed consent.

Quality of life, adherence, concomitant treatment, hospitalization for any causes, cardiovascular functionality will be measured 24 months after the prescription of tafamidis. Twelve months before the index date, treatments, and frequency of hospitalization for any causes will be measured (Table 1).

There will be two sources of information. Clinical and demographic information and death at the baseline will be abstracted from the medical record while the data related to hospitalizations, cardiovascular functionality, quality of life will be collected directly from the patients using validated questionnaires and structured interviews. Thus, in this case the report form (CRF) will serve as a source document.

In patients who have been prescribed with tafamidis more than 1 month and have not received the drug by the HMO yet, the first time of administration of tafamidis will be considered in the analysis. It will be considered as limitation of access. Any delay of supply for treatment will be considered limitation of access which will be assessed during the follow-up.

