9.2. Setting

The study will be performed in approximately 6 Colombian Health Provider Institution (IPS, in its Spanish acronym) whose population includes patients with ATTR-CM diagnosis in the period established. These sites will be in four Colombian cities (Bogotá, Medellin, Cali, and Barranquilla) which have a cardiologist with experience in diagnostic and management of ATTR-CM. The patients can be recruited from the same site or other healthcare institutions, which the site affiliated to the study can invite to participate. In this last scenario, the patients will maintain the clinical care of the original institution, but the information of the study will be collected in the sites affiliated to the study or by their healthcare professionals through virtual interview.

Tafamidis was approved in July 2022 by INVIMA in the treatment of ATTR-CM (14), thus, the patients with diagnosis of ATTR-CM and treated with tafamidis between August 2022 to August 2023 will be invited to participate in the study. At this time, the number of patients expected to participate will be less than 50 patients considering the number of patients diagnosed with ATTR-CM. This cohort study its representative to patients in Colombia without requiring sampling method, considering the estimated number of patients diagnosed with this disease under treatment with tafamidis.

The follow-up period is 24 months since index date with measurement every three months \pm 15 days. During this period quality of life, hospitalization frequency, and death will be measured. The endpoint of the study will be death. Additionally, adherence will be measured. For the cardiovascular functionality, it will be abstracted from the medical records 6MWT and scintigraphy during the time of study.

The activities will be included in the following table.

PFIZER CONFIDENTIAL

CT24-WI-GL02-RF01 6.0 Non-Interventional Study Protocol Template For Primary Data Collection Study 01-

Aug-2023

Page 22 of 57

**CLINICAL AND MEDICAL CONTROLLED DOCUMENT (CMCD)
REQUIRED FORM/TEMPLATE**

Identifier	Version	Title	Effective Date
CT24-WI-GL02-RF01	6.0	NON-INTERVENTIONAL STUDY PROTOCOL TEMPLATE FOR PRIMARY DATA COLLECTION STUDY	01-Aug-2023

Table 1 List of activities

Visit Identifier	Screening	Month ± 15 days										End of Observation
		-12	0	3	6	9	12	15	18	21	24	
Visit Window												
Informed consent	X											
Medical history	X											
Demographic		X										
Clinical variable		X										

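### Mortality counted from first prescription includes months that every enrolled patient must have survived, so it is biased low; the cohort is also not representative as stated

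*Protocol*

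**What the plan says.** Section 9.1 sets time zero: "The index date will be defined as the date for the first prescription of tafamidis". Section 9.2 sets the duration: "The follow-up period is 24 months since index date with measurement every three months", and lists quality of life, hospitalisation frequency and death as measured over that period. It adds: "The endpoint of the study will be death". Section 7 also names mortality among the things the study intends to measure.

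The eligibility window is worded in two ways. Section 9.1: "The patients that were prescribed with tafamidis before August of 2023 will be recruited". Section 9.2: patients "treated with tafamidis between August 2022 to August 2023 will be invited to participate in the study". Entry requires signed consent (Section 9.2.1), and Section 6 gives the start of data collection as "15 November 2023". For patients prescribed before the study starts, Section 9.1 has earlier information collected from what the patient provides.

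On generalisability, Section 9.2 says: "This cohort study its representative to patients in Colombia without requiring sampling method", and supports this by the estimated number of treated patients.

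On the source of death data, the Abstract says that "quality of life, and deaths will be collected directly from the patients using validated questionnaires and structured interviews", whereas Section 9.1 places death with the items taken from the medical record. Table 2 has no row for death.

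**The concern.** A patient prescribed in the window who died before being invited cannot sign consent and so cannot appear in the study. Those who do appear bring months from prescription to consent during which death was impossible by construction. If those months count as follow-up for death, the denominator is inflated and the early deaths are missing from the numerator.

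This is not confined to a few early patients. Data collection runs from 15 November 2023 to 30 July 2025, about 20.5 months, so nobody can have 24 months of prospective follow-up. Every participant's 24 months must include pre-consent time.

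At stake is a two-year mortality figure for treated patients that looks better than the truth, from a study without a comparator, under a sentence presenting the cohort as representative of the country.

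**Working it through.** The protocol states no expected mortality, so there is no figure of its own to reproduce.

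**Lag from index date to the earliest entry** (days to 15 November 2023 ÷ 30.4375), taking the start of data collection as the earliest consent date:
- 1 August 2022: 471 days = 15.5 months
- 31 July 2023 (window in 9.1): 107 days = 3.5 months
- 31 August 2023 (widest reading of 9.2): 76 days = 2.5 months

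These are minimum lags, since consent may come later.

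**Assumptions.** Constant hazard λ, calibrated to the 29.5% mortality at 30 months on tafamidis quoted in Section 7; prescriptions spread evenly over the window; consent on 15 November 2023 if alive; no stopping of follow-up other than death. Fifty eligible patients for illustration (9.5 says close to fifty, 9.2 says fewer).

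**Mortality, lag L from 3.5 to 15.5 months.**
- λ = −ln(1 − 0.295)/30 = 0.01165 per month
- True 24-month mortality = 1 − exp(−24λ) = 24.4%
- Mean probability of surviving to entry = [exp(−3.5λ) − exp(−15.5λ)]/(12λ) = 0.896, so 10.4% die before they can enrol: 5.2 of 50
- Mortality by month 24 among the enrolled = 1 − exp(−24λ)/0.896 = 1 − 0.756/0.896 = 15.6%
- Mean time per enrolled patient: 9.36 months before consent, 13.40 months after
- Rate with time counted from index = 0.1561/(9.36 + 13.40) × 1200 = 8.23 per 100 patient-years
- Rate with time counted from consent = 0.1561/13.40 × 1200 = 13.98 per 100 patient-years, the true value under this model
- Ratio 8.23/13.98 = 0.59; share of counted time that is immortal = 9.36/22.76 = 41%

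**Sensitivity to the assumed mortality and to the window:**

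| Mortality at 30 months | True at 24 months | Enrolled, lag 3.5–15.5 | Enrolled, lag 2.5–15.5 | Naive rate ÷ true rate |
|---|---|---|---|---|
| 15% | 12.2% | 7.6% | 7.8% | 0.60–0.62 |
| 29.5% | 24.4% | 15.6% | 16.1% | 0.59–0.61 |
| 40% | 33.5% | 22.0% | 22.7% | 0.58–0.60 |

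The result depends on when patients were prescribed. At 29.5%, if everyone had a lag of 3.5 months the enrolled figure would be 21.2%; at 15.5 months it would be 9.4%.

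**Hospitalisation.** In a simulation of 2,000,000 patients, a gamma frailty (variance 0 to 1) was shared between death and admission. The naive admission rate divided by the true rate was:
- 1.00 to 0.97 if all pre-consent admissions are captured
- 0.79 to 0.76 if half are captured
- 0.59 to 0.56 if none are captured but time still runs from the index date

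**Does the protocol deal with it?**
- Section 9.1 says the prescription date, the start date and the time of first quality-of-life measurement will be considered in the analysis. It names no method.
- Section 9.7.3.2 lists a subgroup by time on tafamidis before enrolment. This compares survivors with survivors and cannot bring back those who never enrolled.
- Section 9.9 mentions treatment before the study only as a difficulty for baseline quality of life.
- Checklist item 7.2 marks selection bias as not applicable, while item 12.1.1 says Section 9.9 discusses it. It does not.

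**The case against.** The strongest reply is that mortality is in none of the listed objectives and that Section 9.7 plans no death proportion, rate or survival curve. The naive estimator is thus inferred from 9.2, and an analysis plan that is not shown could specify delayed entry. That stands as a limit on severity. It does not remove the point: 9.2 calls death the endpoint and measures it over 24 months from prescription, and an analysis plan cannot withdraw the representativeness sentence or settle two conflicting sources for death.

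A reader might infer that hospitalisation suffers the same immortal-time bias. The documents do not support that. A patient can be admitted before consent and still enrol, and Section 9.1 has earlier information collected retrospectively. With full capture, survivor selection costs 0 to 3% in the simulation. The larger risk is incomplete recall, and Section 9.9 already concedes that completeness depends on the records patients provide.

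A reader might also infer that deaths go unrecorded altogether. After consent they do not: Section 11 makes a fatal event a serious adverse event, and all such events go on the CRF. What remains is the conflict over source and the missing Table 2 row.

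It can fairly be said that the representativeness sentence rests on the small number of treated patients and does not claim to cover everyone with the disease. Even so, the cohort is only those treated patients who lived to be invited and agreed.

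Finally, a left-truncated curve has nobody at risk before the shortest lag, and early risk sets will be very small with fewer than 50 patients. That is correct and limits what the fix can deliver.

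**Conclusion.** The point holds for mortality and for the representativeness sentence. Under the assumed 29.5% at 30 months, a summary from the index date would show about 16% mortality at 24 months where the truth is 24.4%, and a death rate about 0.6 of the true rate. The direction follows from the design. The size rests on a constant hazard borrowed from the trial quoted in Section 7, even prescribing over the window and entry at the earliest possible date; follow-up that ends when treatment stops is ignored. Across 15% to 40% mortality at 30 months the rate ratio stays between 0.58 and 0.62.

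Hospitalisation has a different and conditional problem: under-capture of recalled admissions, plus slight survivor selection. The primary quality-of-life result is exposed through the selection of survivors, which these figures do not quantify.

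This should be fixed. It is not graded higher because mortality appears in the rationale and in 9.2 but in no listed objective.

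**What to change.** 1. In 9.2 and 9.7, count patients at risk of death only from consent, with delayed entry on the time-since-index scale. Report deaths per patient-year from consent, and state that any survival curve is conditional on surviving to the earliest entry time. Reconcile the two eligibility windows in 9.1 and 9.2.
2. Report hospitalisations per patient-year separately for pre-consent (recalled) and post-consent time.
3. Limit the representativeness sentence to surviving, consenting patients and add survivor selection to 9.9. Align checklist items 7.2 and 12.1.1. Where sites can, report how many patients prescribed in the window died or stopped before invitation.
4. Reconcile the Abstract and 9.1 on the source of death data, add date of death to Table 2, and say whether death is an outcome or only an end of follow-up.

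The cost is a few sentences, one CRF field and, where feasible, an aggregate count per site. The downside is mortality figures that are less favourable and less precise.

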9.2.1. Inclusion criteria

Patients must meet all of the following inclusion criteria to be eligible for inclusion in the study:

- Patient older than 18 years
- Spanish speaking patients
- Diagnosis of ATTR-CM confirmed by a Cardiologist
- Prescribed with tafamidis
- Evidence of a personally signed and dated informed consent document indicating that the patient (or a legally acceptable representative) has been informed of all pertinent aspects of the study.

9.2.2. Exclusion criteria

Patients meeting any of the following criteria will not be included in the study:

- Liver or heart transplantation history
- Pregnancy

PFIZER CONFIDENTIAL

CT24-WI-GL02-RF01 6.0 Non-Interventional Study Protocol Template For Primary Data Collection Study 01-

Aug-2023

Page 23 of 57

**CLINICAL AND MEDICAL CONTROLLED DOCUMENT (CMCD)
REQUIRED FORM/TEMPLATE**

Identifier	Version	Title	Effective Date
CT24-WI-GL02-RF01	6.0	NON-INTERVENTIONAL STUDY PROTOCOL TEMPLATE FOR PRIMARY DATA COLLECTION STUDY	01-Aug-2023

- Breastfeeding
- Recruited in clinical trials

9.3. Variables

Table 2 List of variables

Variable	Role	Data source(s)	Operational definition
Date of birth	Demographic characteristics	Medical record, Interview	dd-mm-yyyy
Age	Demographic characteristics	Medical record, Interview	Time elapsed since the time of birth to signed consent form (years)
Sex assigned at birth	Demographic characteristics	Medical record, Interview	Men, female
Race (ethnicity)	Demographic characteristics	Medical record, Interview	Indigenous, Rrom, Black, None and Other
Date of symptoms of ATTR-CM	Clinical characteristic	Medical record, Interview	dd-mm-yyyy
Date of ATTR-CM diagnosis	Clinical characteristic	Medical record, Interview	dd-mm-yyyy
Genotype	Clinical characteristic	Medical record, Interview	ATTRwt; ATTRv
Scintigraphy at diagnosis (Perugini scale)	Clinical characteristic	Medical record,	Grade 0 – 3
Biopsy	Clinical characteristic	Medical record, Interview	Yes, No
Sampling biopsy	Clinical characteristic	Medical record, Interview	Heart, bone marrow, others
Sum of QRS amplitude in I, II, and III leads at diagnosis	Clinical characteristic	Medical record, Interview	mm
Sum of QRS amplitude in all six limb leads at diagnosis	Clinical characteristic	Medical record, Interview	mm
Sum of QRS amplitude in all six precordial leads at diagnosis	Clinical characteristic	Medical record, Interview	mm
Sokolow-Lyon index low voltage criteria at diagnosis	Clinical characteristic	Medical record, Interview	mm
Low QRS voltage at diagnosis	Clinical characteristic	Medical record, Interview	Yes, No

PFIZER CONFIDENTIAL

CT24-WI-GL02-RF01 6.0 Non-Interventional Study Protocol Template For Primary Data Collection Study 01-

Aug-2023

Page 24 of 57

**CLINICAL AND MEDICAL CONTROLLED DOCUMENT (CMCD)
REQUIRED FORM/TEMPLATE**

Identifier	Version	Title	Effective Date
CT24-WI-GL02-RF01	6.0	NON-INTERVENTIONAL STUDY PROTOCOL TEMPLATE FOR PRIMARY DATA COLLECTION STUDY	01-Aug-2023

Pseudo-infarct Q waves at diagnosis	Clinical characteristic	Medical record, Interview	Yes, No
Atrioventricular conduction disease (block) at diagnosis	Clinical characteristic	Medical record, Interview	Yes, No
Genetic counseling	Patient	Medical record, Interview	Yes, No
Left ventricular ejection fraction at diagnosis	Clinical characteristic	Medical record, Interview	%
N-terminal pro b-type natriuretic peptide at diagnosis	Clinical characteristic	Medical record, Interview	(pg/mL)
Heart failure at early age	Clinical characteristic	Medical record, Interview	Yes, No
Any cardiac arrhythmias or conduction disorders	Clinical characteristic	Medical record, Interview	Yes, No
Type of any cardiac arrhythmias or conduction disorders	Clinical characteristic	Medical record, Interview	Cardiac arrhythmias, Cardiac arrest, Paroxysmal tachycardia, Atrial fibrillation and flutter, Conduction disorders, Atrioventricular and left bundle branch block, other conduction disorders
Lumbar spinal stenosis	Clinical characteristic	Medical record, Interview	Yes, No
Hypertrophic cardiomyopathy over 60 years old	Clinical characteristic	Medical record, Interview	Yes, No
Embolic stroke	Clinical characteristic	Medical record, Interview	Yes, No
Low flow/low gradient aortic valve stenosis	Clinical characteristic	Medical record, Interview	Yes, No
Diabetes mellitus	Clinical characteristic	Medical record, Interview	Yes, No
Hypertension	Clinical characteristic	Medical record, Interview	Yes, No
Sleep apnea	Clinical characteristic	Medical record, Interview	Yes, No
Chronic Kidney Diseases	Clinical characteristic	Medical record, Interview	Yes, No
Any cardiovascular device	Clinical characteristic	Medical record, Interview	Yes, No
Which any cardiovascular devices	Clinical characteristic	Medical record, Interview	Cardiac resynchronization

PFIZER CONFIDENTIAL

CT24-WI-GL02-RF01 6.0 Non-Interventional Study Protocol Template For Primary Data Collection Study 01-

Aug-2023

Page 25 of 57

**CLINICAL AND MEDICAL CONTROLLED DOCUMENT (CMCD)
REQUIRED FORM/TEMPLATE**

Identifier	Version	Title	Effective Date
CT24-WI-GL02-RF01	6.0	NON-INTERVENTIONAL STUDY PROTOCOL TEMPLATE FOR PRIMARY DATA COLLECTION STUDY	01-Aug-2023

			therapy – defibrillator (CRT-D), Cardiac resynchronization therapy – pacemakers (CRT-P), implantable cardioverter defibrillator (ICD)
History of heart block	Clinical characteristic	Medical record, Interview	Yes, No
NYHA FC	Clinical characteristic	Medical record, Interview	I, II, III, IV
Syncope	Clinical characteristic	Medical record, Interview	Yes, No
Carpal tunnel syndrome	Clinical characteristic	Medical record, Interview	Yes, No
Bleeding history	Clinical characteristic	Medical record, Interview	Yes, No
Intracardiac thrombosis	Clinical characteristic	Medical record, Interview	Yes, No
Stroke	Clinical characteristic	Medical record, Interview	Yes, No
Polyneuropathy	Clinical characteristic	Medical record, Interview	Yes, No
Orthostatic hypotension	Clinical characteristic	Medical record, Interview	Yes, No
Erectile dysfunction	Clinical characteristic	Medical record, Interview	Yes, No
Glaucoma	Clinical characteristic	Medical record, Interview	Yes, No
Intravitreal deposition	Clinical characteristic	Medical record, Interview	Yes, No
angiotensin-converting enzyme inhibitors previous diagnosis	Treatment	Medical record, Interview	Yes, No
Agents acting on the renin-angiotensin system previous diagnosis	Treatment	Medical record, Interview	Yes, No
HMG COA reductase inhibitors previous diagnosis	Treatment	Medical record, Interview	Yes, No
Loop diuretics previous diagnosis	Treatment	Medical record, Interview	Yes, No
Amiodarone previous diagnosis	Treatment	Medical record, Interview	Yes, No

PFIZER CONFIDENTIAL

CT24-WI-GL02-RF01 6.0 Non-Interventional Study Protocol Template For Primary Data Collection Study 01-

Aug-2023

Page 26 of 57

**CLINICAL AND MEDICAL CONTROLLED DOCUMENT (CMCD)
REQUIRED FORM/TEMPLATE**

Identifier	Version	Title	Effective Date
CT24-WI-GL02-RF01	6.0	NON-INTERVENTIONAL STUDY PROTOCOL TEMPLATE FOR PRIMARY DATA COLLECTION STUDY	01-Aug-2023

Anticoagulation previous diagnosis	Treatment	Medical record, Interview	Yes, No
Beta blockers previous diagnosis	Treatment	Medical record, Interview	Yes, No
Calcium channel blockers previous diagnosis	Treatment	Medical record, Interview	Yes, No
Angiotensin receptor blockers previous diagnosis	Treatment	Medical record, Interview	Yes, No
Agents acting on the renin–angiotensin system after diagnosis*	Treatment	Medical record, Interview	Yes, No
HMG COA reductase inhibitors after diagnosis*	Treatment	Medical record, Interview	Yes, No
Loop diuretics after diagnosis *	Treatment	Medical record, Interview	Yes, No
Amiodarone after diagnosis*	Treatment	Medical record, Interview	Yes, No
Anticoagulation after diagnosis *	Treatment	Medical record, Interview	Apixaban, dabigatran, rivaroxaban, warfarin
Beta blockers after diagnosis*	Treatment	Medical record, Interview	Yes, No
Calcium channel blockers after diagnosis*	Treatment	Medical record, Interview	Yes, No
Angiotensin receptor blockers after diagnosis*	Treatment	Medical record, Interview	Yes, No
angiotensin-converting enzyme inhibitors previous diagnosis*	Treatment	Medical record, Interview	Yes, No
Glomerular filtration rate at diagnosis*	Clinical characteristics	Medical record, Interview	>40, <40
Cardiovascular devices during follow-up	Treatment	Medical record, Interview	Cardiac resynchronization therapy – defibrillator (CRT-D), Cardiac resynchronization therapy – pacemakers (CRT-P), implantable cardioverter defibrillator (ICD)
Date of prescription of tafamidis	Treatment	Interview	ddmm/yyyy

PFIZER CONFIDENTIAL

CT24-WI-GL02-RF01 6.0 Non-Interventional Study Protocol Template For Primary Data Collection Study 01-

Aug-2023

Page 27 of 57

**CLINICAL AND MEDICAL CONTROLLED DOCUMENT (CMCD)
REQUIRED FORM/TEMPLATE**

Identifier	Version	Title	Effective Date
CT24-WI-GL02-RF01	6.0	NON-INTERVENTIONAL STUDY PROTOCOL TEMPLATE FOR PRIMARY DATA COLLECTION STUDY	01-Aug-2023

Date of first administration of tafamidis	Treatment	Interview	ddmm/yyyy
Delay of supply of tafamidis	Treatment	Interview	Yes, No
Cause of delay	Treatment	Interview	Authorization, Treatment not available in the supplier, error of prescription, other
Adherence	Outcomes	Interview	%
Sum of QRS amplitude in I, II, and III leads at the end of follow-up	Clinical characteristic	Medical record, Interview	mm
Sum of QRS amplitude in all six limb leads at the end of follow-up	Clinical characteristic	Medical record, Interview	mm
Sum of QRS amplitude in all six precordial leads at the end of follow-up	Clinical characteristic	Medical record, Interview	mm
Sokolow-Lyon index low voltage criteria at the end of follow-up	Clinical characteristic	Medical record, Interview	mm
Persistence	Outcomes	Interview	Yes, No
Hospitalization	Outcomes	Interview	Yes, No
Cause of the hospitalization	Outcomes	Interview	Cardiovascular, Other
Date of hospitalization	Outcomes	Interview	Date of admission: dd-mm-yyyy Date of discharge: dd-mm-yyyy
Day(s) of hospitalization	Outcomes	Interview	Days
Quality of life (KCCQ-OS score per visit)	Outcomes	Interview	Score
6MWT [§]	Outcomes	Site	Meters
Scintigraphy (Perugini scale) [§]	Outcomes	Site	Grade 0 - 3

* Per visits, according to schedule of the study

§ According to medical criteria, considering that the physician may choose to perform a different test

PFIZER CONFIDENTIAL

CT24-WI-GL02-RF01 6.0 Non-Interventional Study Protocol Template For Primary Data Collection Study 01-

Aug-2023

Page 28 of 57

**CLINICAL AND MEDICAL CONTROLLED DOCUMENT (CMCD)
REQUIRED FORM/TEMPLATE**

Identifier	Version	Title	Effective Date
CT24-WI-GL02-RF01	6.0	NON-INTERVENTIONAL STUDY PROTOCOL TEMPLATE FOR PRIMARY DATA COLLECTION STUDY	01-Aug-2023

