9.5. Study size

Sample size is not required for being observational and descriptive study. The expected number of patients eligible for the study is close to fifty considering the number of patients identified with the diagnosis and the access to the treatment based on the national database of MiPres in Colombia in which each prescription of treatments outside of National Formulary must be registered (19).

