9.7. Data analysis

9.7.1. Statistical Hypotheses

This is a descriptive, prospective, and observational study. There is no formal hypothesis being tested. The study will describe the clinical and demographic characteristics of ATTR-CM patients. Also, it will describe previous treatments, cardiovascular devices, and comorbidities.

Adherence, persistence, and frequency of hospitalization will be described during the time exposure of treatment.

The change of baseline in the quality of life measured every 3 and 6 months respectively for 24 months.

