9.7.5.1. Descriptive statistics

Frequencies and percentages will be reported for binary and categorical variables, while medians and interquartile ranges (IQRs) will be reported for continuous variables, i.e., HRU. Finally, it will be presented through a tabular display of summary statistics and will be complemented by the generation of graphs, such as histograms, box plots, violin plots, density plots, scatterplots, depending on the nature of the variable.

On the other hand, difference of means (Student or Welch t-test) or medians (Wilcoxon or Kruskal-Wallí's test) between subgroups will be considered (according to the variable distribution – normal or not), considering the sizes of these groups and trends in the behavior of the measures of centrality and dispersion.

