9.7.5.2. Bivariate and multivariable analysis

This study does not evaluate any hypothesis. As exploratory analysis and if it is feasible with the number of patients enrolled and distribution of the studied variables, the analysis of the association of baseline characteristics with quality of life and cardiovascular functionality using bivariate and multivariate regression models will be conducted. In terms of distribution of studied continuous variables, a normal test will be conducted in order to determine if it requires a parametric or no parametric test. The test of normality used will be used, frequency distribution (histogram), boxplot, P-P plot (probability-probability plot), and Q-Q plot

PFIZER CONFIDENTIAL

CT24-WI-GL02-RF01 6.0 Non-Interventional Study Protocol Template For Primary Data Collection Study 01-

Aug-2023

Page 33 of 57

CLINICAL AND MEDICAL CONTROLLED DOCUMENT (CMCD) REQUIRED FORM/TEMPLATE

Identifier	Version	Title	Effective Date
CT24-WI-GL02-RF01	6.0	NON-INTERVENTIONAL STUDY PROTOCOL TEMPLATE FOR PRIMARY DATA COLLECTION STUDY	01-Aug-2023

(quantile-quantile plot) to assess normality visually and Kolmogorov-Smirnov (K-S) test and Shapiro-wilk test to evaluate directly (20).

For bivariate analysis, no-parametric tests are necessary due to the variables being of dependent nature by being repeated measures during the follow-up. For continuous variables, paired t-test and Wilcoxon signed ranks test will be used (21).

For multivariable analysis, mixed models will be used, repeated measures analysis of covariance with an unstructured covariance matrix, being patient as random effects and visit and baseline characteristics as fixed effects (22,23).

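### Table 2 records GFR at diagnosis only as >40 or <40, with no unit: a value of exactly 40 has no code, and a continuous measure is dichotomised at data capture

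*Protocol*

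**What the plan says.** In Protocol Section 9.3, Table 2, the row "Glomerular filtration rate at diagnosis" has the role of a clinical characteristic and is sourced from the medical record and interview. Its whole operational definition is two codes, >40 and <40. There is no equality sign on either side, no unit and no numeric field. The row carries an asterisk, which the table's footnote explains as "Per visits, according to schedule of the study".

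Elsewhere in the same table, "N-terminal pro b-type natriuretic peptide at diagnosis" is recorded in pg/mL, LVEF in % and the QRS sums in mm. The only other renal item is "Chronic Kidney Diseases", recorded as yes or no.

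On analysis:

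- Section 9.7.5.1 states that "medians and interquartile ranges (IQRs) will be reported for continuous variables".
- Section 9.7.3.2 lists clinical characteristics, generically, among the subgroups.
- Section 9.7.5.2 says that, as an exploratory step and if patient numbers and distributions allow, "the analysis of the association of baseline characteristics with quality of life and cardiovascular functionality using bivariate and multivariate regression models will be conducted". GFR is not named there.
- Section 9.5 says "The expected number of patients eligible for the study is close to fifty".
- Section 9.7.1 says "There is no formal hypothesis being tested".

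**The concern.** The row has two faults that can be seen without any assumption.

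First, the codes are not exhaustive. A site that reads 40 in the chart must leave the field empty, choose a side, or wait for a query, and different sites may choose differently.

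Second, the cut is made in the variable definition and not in the analysis. An SAP can derive two groups from a number, but it cannot derive a number from two groups. Values of 41 and 90 become identical, as do 39 and 12. With a yes/no item for chronic kidney disease already in the table, GFR is the one place where graded renal function could be held, and no reason is given for treating it differently from LVEF or NT-proBNP.

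What is at stake is a proper baseline description of renal function (a secondary objective describes clinical characteristics) and the usefulness of GFR as a candidate predictor in a cohort of about 50. The row also does not settle when GFR is measured: its name places it at diagnosis, while its footnote places it at every visit.

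**Working it through.** The protocol states no figure for this point, so there is nothing to reproduce. The check has three parts.

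**1. Category gap, by reading.** Values of 39, 40 and 41 map to <40, no code, and >40.

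**2. Information kept by the cut.** Inputs: N = 50 (Section 9.5). The share p of patients below 40 is not given, so it is an assumption and is varied. For a normal predictor with a linear effect on the outcome, the efficiency of a two-group version relative to the numeric value is

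efficiency = φ(z)² / [p(1 − p)], with z the cut on the standard normal scale and p = Φ(z).

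Worked cases:

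- p = 0.50: z = 0, φ = 0.399, efficiency = 0.159 / 0.25 = 0.637, loss 36%. This is the smallest possible loss.
- p = 0.20: z = −0.842, φ = 0.280, efficiency = 0.0784 / 0.16 = 0.490, loss 51%.

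| Share below 40 | Efficiency | Loss | Equivalent N of 50 |
|---|---|---|---|
| 50% | 0.637 | 36% | 31.8 |
| 40% | 0.622 | 38% | 31.1 |
| 30% | 0.576 | 42% | 28.8 |
| 25% | 0.539 | 46% | 26.9 |
| 20% | 0.490 | 51% | 24.5 |
| 15% | 0.426 | 57% | 21.3 |
| 10% | 0.342 | 66% | 17.1 |
| 5% | 0.224 | 78% | 11.2 |

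A loss of exactly 50% needs about 21% of patients below 40. A loss between 45% and 55% needs about 17-26%.

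To turn this into a range, assume GFR is normal with mean 50-60 and SD 15-20. Then z = (40 − mean)/SD runs from −0.50 at (50, 20) to −1.33 at (60, 15), and efficiency falls as z moves away from zero, so these two corners give the extremes:

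- (50, 20): p = 0.309, loss 0.419, efficiency 0.581, equivalent N = 50 × 0.581 ≈ 29.
- (60, 15): p = 0.091, loss 0.675, efficiency 0.325, equivalent N = 50 × 0.325 ≈ 16.

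**3. Patients at exactly 40.** Assume whole-number recording and the same means and SDs:

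P(40) = Φ((40.5 − mean)/SD) − Φ((39.5 − mean)/SD), and P(at least one of 50) = 1 − (1 − P(40))⁵⁰.

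- Highest, (50, 15): P(40) = 0.0213; expected 50 × 0.0213 = 1.06 patients; chance of at least one 66%.
- Lowest, (60, 15): P(40) = 0.0109; expected 0.55 patients; chance of at least one 42%.

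**The case against.** The strongest reply is that little depends on this row. Section 9.7.5.2 is exploratory, runs only if feasible and does not name GFR. Section 9.7.3.2 does not name it either, and GFR is absent from the abstract's variable list. No hypothesis is tested, so no stated power is lost. The boundary gap concerns about one patient or fewer, and Section 9.8 provides for missing or inconsistent data to be queried with the sites, so such a patient need not end up missing. If an equality sign has simply dropped out of the cell, the gap closes. All of this stands as a limit on the consequence. It does not supply the unit or undo the cut.

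Two stronger readings are tempting, and the documents do not support them:

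- A reader might infer that the cut costs half of the information. That is a conditional result. It needs roughly 17-26% of patients below 40, and the protocol gives neither that share nor any GFR distribution.
- A reader might infer that the numeric GFR is lost for good. Section 9.6.1 names charts as the usual source documents, and Section 9.6.2 requires records to be kept for at least 15 years. A number in the chart is missing from the planned dataset but can be re-abstracted. That is still extra work, because Section 9.4 relies on medical records provided by the patient.

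The CRF is also not part of the protocol. That GFR is captured only as two categories rests on Table 2.

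**Conclusion.** The point holds as a minor but real defect in a variable definition. Certain from the text: the two codes leave 40 unclassified, no unit is given, a continuous measure is dichotomised while comparable measures stay numeric, the planned median and IQR cannot be produced for it, and the row's name conflicts with its per-visit footnote.

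Conditional on GFR entering the exploratory regression, and on a normal predictor with a linear effect: the loss is at least about 36%, and 42-68% (efficiency 0.32-0.58) if the mean is 50-60 and the SD 15-20. On the same assumed distribution with whole-number recording, the chance that at least one of 50 patients has no category is 42-66%. These ranges follow from the assumptions and are not trial data.

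The primary description of KCCQ over two years is not affected.

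**What to change.** In Table 2, replace the two codes with a numeric GFR field that carries its unit and measurement date, and keep GFR numeric in the dataset. If a two-group table is wanted, derive it at analysis with exhaustive categories that assign the boundary value to one side. Reconcile the diagnosis-time name of the row with its per-visit asterisk, so that sites know whether to collect GFR once or repeatedly.

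The cost is one CRF field changed from a tick box to a number taken from the medical record, with no extra test. Made before data capture this is nearly free; made later, it means returning to the source records of every enrolled patient.
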